2.2.15 Safety Analyses

Safety analyses will be based on the Safety Population and be presented by treatment groups. Only descriptive statistics will be presented and inferential statistical testing will not be performed.

2.2.15.1 Extent of Exposure and Compliance

Extent of exposure to study medication will be tabulated by treatment group. Duration of exposure will be calculated as last day of exposure minus the first day of exposure +1. Exposure will be summarized by treatment group for the safety population.

Compliance will be assessed by pill counts. The number of tablets dispensed and the number of tablets returned will be calculated. Compliance will be calculated by subtracting the number of returned

tablets (number of tablets taken) from the number of tablets dispensed (minus extra tablets dispensed) and then dividing the difference by the number of tablets that should have been taken (two for each day on study). The result will be multiplied by 100%. Compliance will be calculated over the entire duration of exposure.

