8.3 Study Drug Administration

Study drug is to be administered only to subjects who have provided written informed consent and have met the criteria outlined in [Sections 7.1 and 7.2](#). Study drug will be administered orally once daily for 12 weeks. ([Table 3](#)).

Table 3. Study Drug Dosing

Study Drug Group	Dose	Treatment Regimen
AQX-1125 200 mg	2 AQX-1125 100 mg tablets	2 tablets, once daily
Placebo	2 placebo tablets	

The first dose of study drug will be administered in the clinic at Baseline (Visit 2), once all Baseline procedures are completed and the subject has been randomized. No investigational or commercial agents or therapies other than those described in [Section 8.1.1](#) may be administered with the intention to treat the subject's condition.

Subjects will be instructed to take the study drug with a glass of water around the same time of day with food, or eat a light meal no more than 4 hours prior to consumption, for 12 weeks. On study visit days, subjects will be instructed not to take the study drug before the visit and to eat a light meal no more than 2 hours prior to the scheduled visit. The study drug will be taken during the study visit after all assessments have been completed. If the subject has inadvertently taken the study drug prior to attending the clinic, the clinic dose should not be given.

If a dose is missed, subjects should take the dose as soon as they remember on the same day. However, if it is the next day, the missed dose should be skipped and next dose taken as normal. Only 1 dose of study drug (2 tablets) should be taken each day and a double dose should not be taken.

Remaining unused study drug will be collected at Week 6 and at the end of the 12-week treatment. Subjects will be instructed to return all used wallets (including partially used and those with unused spare doses) for reconciliation at each study visit.

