8.6 Study Drug Packaging

The tablets are packaged in blister packs, with 2 blister packs containing a total of a 14-day supply and 2 spare doses, assembled into a child-resistant cardboard wallet. Based on a dosing regimen of 2 tablets a day, the wallet design will contain a total of 32 tablets/16 doses.

[figure not shown]

Figure 2. Tablet packaging

Sufficient quantities of wallets will be dispensed to enable the subject to continue to take the medication up to the next study visit. The spare doses will allow the subjects to remain on treatment if their visit is a few days post the target visit date but within predefined acceptable windows.

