8.10 Treatment and Electronic Diary Compliance

Treatment compliance will be assessed through tablet counts. The subject will be instructed to bring all dispensed wallets back to the clinic at each visit (even if the wallet is empty). The number of used and remaining tablets will be recorded on the eCRF.

Subject compliance with the eDiary will be monitored by trained study site personnel at each study visit.

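### The SAP compliance formula takes unused spare tablets off twice when they are returned, so a fully adherent on-schedule completer would be reported at about 86%

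*SAP*

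**What the plan says.** SAP 2.2.15.1 assesses compliance by pill count. The numerator is formed by subtracting returned tablets "from the number of tablets dispensed (minus extra tablets dispensed) and then dividing the difference". A bracket placed after the returned tablets describes them as the tablets taken. The divisor is a daily requirement, worded "by the number of tablets that should have been taken (two for each day on study", and the quotient is put on a percentage scale. The section then adds: "Compliance will be calculated over the entire duration of exposure". It does not define the extra tablets.

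The protocol supplies the rest:

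- Section 8.6: the tablets come in wallets, "with 2 blister packs containing a total of a 14-day supply and 2 spare doses", and "the wallet design will contain a total of 32 tablets/16 doses". The number of wallets per visit is not given, only that supply must last until the next visit.
- Section 8.3: subjects are told to "return all used wallets (including partially used and those with unused spare doses) for reconciliation at each study visit".
- Section 8.10: "The number of used and remaining tablets will be recorded on the eCRF". No separate count of spares is mentioned.

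**The concern.** As written, the numerator is (dispensed - extra) - returned. An unused spare tablet is in the dispensed count and, once brought back, in the returned count. Dispensed minus returned therefore already leaves it out of the tablets taken. Deducting extra tablets as well removes it a second time.

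Compliance is the trial's reported measure of adherence. In a Phase 2 trial, an apparent figure in the mid-80s in subjects who took every dose could lead a reader to blame a null result on poor adherence. Use of the spares would also be hidden.

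Two further faults sit in the same short text. The bracket after returned tablets describes them as tablets taken, which is the opposite quantity. The denominator counts days on study, while the closing sentence sets the period as the duration of exposure.

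**Working it through.** **Inputs.** Two tablets a day for 12 weeks, so 84 days and 168 tablets due (protocol 8.3). Each wallet holds a 14-day supply plus 2 spare doses (protocol 8.6). Visit 4 is at day 84 ± 3 (protocol Table 1). Two assumptions: three wallets per 42-day interval, six in all, inferred from the 14-day supply; and extra tablets means the packaged spares.

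**The plan's own figure.** Tablets per wallet: 2 x (14 + 2) = 32, or 16 doses, as stated. Of these, 28 are scheduled and 4 are spare. The SAP gives no worked compliance value to reproduce.

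**Formula as written.** 100 x [(dispensed - extra) - returned]/(2 x days). For a subject who takes every dose and returns everything else:

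| Case | Dispensed | Extra | Returned | Due | Reported |
|---|---|---|---|---|---|
| 6 wallets, 84 days | 192 | 24 | 24 | 168 | 144/168 = 85.7% |
| 6 wallets, 81 days | 192 | 24 | 30 | 162 | 138/162 = 85.2% |
| 6 wallets, 87 days | 192 | 24 | 18 | 174 | 150/174 = 86.2% |
| 7 wallets, 84 days | 224 | 28 | 56 | 168 | 140/168 = 83.3% |
| 8 wallets, 84 days | 256 | 32 | 88 | 168 | 136/168 = 81.0% |
| 3 wallets, stops day 28 | 96 | 12 | 40 | 56 | 44/56 = 78.6% |
| 3 wallets, stops day 21 | 96 | 12 | 54 | 42 | 30/42 = 71.4% |

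A single wallet over 14 days gives 24/28 = 85.7%, so the completer figure does not depend on the total being six, only on supply matching the schedule.

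**Size of the error.** When all unused tablets are returned, the understatement is extra/(2 x days). It is 24/168 = 14.3 points at 84 days, 24/162 = 14.8 at 81 and 24/174 = 13.8 at 87. For the early stoppers above it is 12/56 = 21.4 and 12/42 = 28.6.

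**Other adherence levels, 6 wallets and 84 days.**

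- 151 tablets taken (true 89.9%): (192 - 24 - 41)/168 = 75.6%.
- 134 taken (true 79.8%): (192 - 24 - 58)/168 = 65.5%.
- All 192 taken (true 114.3%): (192 - 24 - 0)/168 = 100.0%.

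**The bracket taken literally.** Subtracting tablets taken instead of tablets returned gives the perfect completer (192 - 24 - 168)/168 = 0%.

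**The denominator.** Take a subject who is adherent to day 42, stops drug and stays to day 84. With the numerator corrected, compliance is 84/84 = 100% on exposure days and 84/168 = 50% on study days. Protocol 6.1 encourages subjects who stop drug to continue with visits, and section 10.2 assumes 10% discontinuation, so such subjects are expected.

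**Corrected formula.** (dispensed - returned)/(2 x days of exposure) gives 100% in every row of the table; for the completer, (192 - 24)/168 = 100%.

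**The case against.** The strongest reply is that the terms are loose rather than the arithmetic wrong. If the returned count were meant to leave out spares, the completer would score (192 - 24 - 0)/168 = 100%. Neither document says so, and protocol 8.3 and 8.10 point the other way.

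The double removal does depend on the spares coming back. A subject who takes 168 tablets and keeps the 24 spares gets 100% from the SAP formula, which is right, while dispensed minus returned would give 192/168 = 114.3%. That part stands, and the fix has to deal with unreturned wallets.

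It is also fair that the closing sentence of 2.2.15.1 probably settles the period as exposure. The denominator conflict is then a wording fault, though one that can halve a subject's figure if it is programmed the other way.

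The reach is limited. Compliance is a descriptive summary under SAP 2.2.15, with no inferential testing. It does not enter the primary model (2.2.13.1) or the multiple-imputation variables (2.2.10.2), which use duration of exposure. The counts are on the eCRF, so the percentage can be recomputed.

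A reader might go further and infer that every compliance figure is too low, that the error is a constant 14.3 points, or that PP membership would be decided on wrong values. The documents support none of these. The first fails when spares are not returned. The second holds only at 24 spares and 84 days. On the third, SAP 2.2.5.3 and 2.2.8 leave PP membership and deviations to blinded review and a separate deviation plan, and neither refers to this percentage.

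**Conclusion.** The formula is wrong as written and should be corrected before it is programmed. Its main result, 85.7% for a perfectly adherent 84-day completer, rests on three conditions: extra tablets means the packaged spares, three wallets are supplied per six-week interval, and all unused spares are returned and counted. Only the last has direct support in the protocol; the other two are reasonable inferences. Under these conditions the understatement stays close to 14 to 15 points for completers, and it grows for subjects who stop early with a large unused supply. If stopping patterns differed between arms, the summary could therefore show an adherence difference that is not real. The consequence ends with that descriptive summary; no efficacy conclusion changes.

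**What to change.** Rewrite the calculation in SAP 2.2.15.1 as: compliance = 100 x (tablets dispensed - tablets returned)/(2 x days of exposure). In detail:

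- Do not subtract spare tablets.
- Delete the bracket that equates returned tablets with tablets taken.
- Change the denominator from days on study to days of exposure, in line with the section's closing sentence.
- Flag subjects with unreturned wallets, for whom this formula would overstate intake.

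The cost is one rewritten SAP sentence and a flag in the compliance output. No new data are needed beyond the tablet counts already collected.

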2.2.15.2 Adverse Events

Counts and percentages of subjects who experienced any of the following will be presented by treatment group and overall: any AE, any drug related AE, discontinuations of study participation due to an AE, any serious adverse events (SAE), deaths, drug related SAEs, and treatment-emergent AE of special interest (TEAESI). Only those adverse events determined to be treatment emergent (TEAE) will be presented. Treatment emergent adverse events are those events with the date and time of AE onset being greater than the date and time of first dosing, and (other than TEAESIs) only those with an onset date within 28 days after the last date of dosing.

Verbatim terms on the case report forms will be linked to preferred terms and related body systems using the MedDRA Coding Dictionary version 20.0. The number and percentage of subjects who experience treatment-emergent adverse events will be tabulated by System Organ Class (SOC) and Preferred Term (PT) by treatment group and overall. Adverse events will be counted only once for a subject within each Preferred Term and System Organ Class; thus, since a subject may have more than one Preferred Term within an SOC, percentages of PT may not sum to the percentage in the SOC. If a subject reports an AE with a Preferred Term multiple times with differing severities, only the most severe is counted. If a subject reports an AE with a Preferred Term multiple times with differing relationships to study medication, only the one related to study drug is counted. Drug-related adverse events are defined as having a causality rating of being probable or possible.

All reported AEs will be tabulated as described above. For the overall AE table, number of adverse events will also be presented. In addition, a tabulation of adverse events that occur at a frequency of 2% or greater in any active treatment group at the SOC or PT level will be prepared.

AEs will also be tabulated by intensity/severity of the event (Grade 1 – mild/ Grade 2 – moderate/ Grade 3 – severe/ Grade 4 – life-threatening or disabling/ Grade 5 - death) and by Investigator's assessment of relationship to study medication (Probable, Possible or Unlikely). Adverse events judged by the Investigator to be Serious Adverse Events

(SAEs), SAEs resulting in death, AEs (regardless of seriousness) that require modification to study medication dosing (interruption or discontinuation) will also be tabulated by SOC and PT.

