9.3.5.6 Recording Adverse Events

For the purposes of this study, any detrimental change in the subject's condition, from signing of informed consent up to completion of the treatment period should be considered an AE (i.e. for up to 28 days after last dose of investigational product has been taken).

AEs should be captured wherever possible as a diagnosis and it is the Investigator's responsibility to ensure this is done. If a precise diagnosis cannot be made, a syndrome can be recorded. Rarely should it be necessary to record one or more individual symptoms.

All ongoing non-ocular AEs should be followed up until the Off-Treatment Safety Follow-up Visit (for 28 days after the last administration of study drug), with the exception of any ongoing study drug-related AEs, which should be followed until resolution, unless in the Investigator's opinion the AE is unlikely to resolve due to the subject's underlying disease. Ongoing ocular AEs will be queried at the Follow-up call 3 months post last dose and at the Ophthalmic Safety Follow-up Visit 6 months post last dose.

Ocular AEs must be followed until the 6-month Ophthalmic Safety Follow-up Visit.

Any new SAEs occurring up to 28 days after the last administration of study drug should be reported to the drug safety manager.

At any time after the Off-Treatment Safety Follow-up Visit, if an Investigator learns of an SAE that can be reasonably related to study drug, he/she should promptly notify the drug safety manager.

All AEs (including SAEs) are to be accurately recorded on the Adverse Event page(s) of the eCRF. The Investigator will carefully evaluate each AE to determine:

- duration (start and end dates)
- intensity (grade)
- seriousness
- relationship to study drug (Unlikely, Possible, Probable)
- action taken with study drug (study drug modification or interruption, study drug discontinuation)
- action taken (none, medication, medical intervention)
- outcome (resolved without sequelae, resolved with sequelae, ongoing)

The Investigator will evaluate all AEs and SAEs with regard to maximum intensity and relationship to study drug. Maximum intensity should be assigned using one of the severity grades as outlined in the National Cancer Institute's Common Terminology Criteria for Adverse Events v4.0. If the AE is not specifically listed in Common Terminology Criteria for Adverse Events v4.0, the following grades will be used:

- Grade 1: mild
- Grade 2: moderate
- Grade 3: severe

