2.2.2 Study Assessment Time Points

All enrolled subjects will record the maximum and average daily pelvic pain in the eDiary from Screening Visit 1 to Week 16, as well as analgesic medication taken each day. Subjects will record 24-hour voiding frequency prior to scheduled visits at baseline, Week 6, Week 12 and Week 16. Visits are scheduled at the following timepoints:

- Visit 1/Screening
- Visit 1a/ Baseline ophthalmic assessments (at any time before Visit 2)
- Visit 2/Baseline (Week 1)
- Visit 3 (Week 6)
- Visit 4 (Week 12)
- Early Termination: Subjects who withdraw from the study during the treatment period should complete an Early Termination Visit. Subjects who discontinue the double-blind treatment for any reason will be encouraged to continue with all subsequent study-related visits and a visit at Week 12 to assess efficacy endpoints.
- Off Treatment (Week 16) 4-week off drug Safety Follow-up period
- Ophthalmic Safety Follow-up Visit 6-months post last dose: Ophthalmic assessments and AE collection (ophthalmic related AEs only)
- Follow-up telephone call 3 months after the last dose: AE collection (ophthalmic related AEs only)
- Unscheduled Visits: Unscheduled visits may occur when subject needs to make a visit in between the scheduled visit dates due to an AE, difficulty complying with the study protocol requirements, or a significant change in their disease state. Unscheduled visits may be conducted at any time during the study and should include the same assessments as Week 16.

| Event | Screening Period ^a | | Baseline | Treatment Period | | ET ^j | Safety Follow-up | | |
|--|-------------------------------|----------------------------|----------|------------------|----------------|-----------------|------------------|-----------------|-----------------------------|
| | Visit 1 | Baseline Ophthal. Visit 1a | | Visit 2 | Visit 3 | | Visit 4 | Off-Treatment | Telephone call ^k |
| Week | | | 1 | 6 | 12 | NA | 16 | 25 | 38 |
| Day (± window) | -14 (±7) | Before Visit 2 | 1 | 42 (±3) | 84 (±3) | NA | 112 (±3) | 175 (±7) | 266 (±7) |
| 24-hour voiding frequency ^h | | | ✓ | ✓ | ✓ | ✓ | ✓ | | |
| AE collection | ✓ | | ✓ | ✓ | ✓ | ✓ | ✓ | ✓ ^l | ✓ ^l |
| Concomitant medications | ✓ | | ✓ | ✓ | ✓ | ✓ | ✓ | | |
| Study drug dispensing ⁱ | | | ✓ | ✓ | | | | | |
| Study drug compliance check | | | | ✓ | ✓ | ✓ | | | |
| Study drug accountability | | | | ✓ | ✓ | ✓ | | | |
| eDiary Issue/Train/Review/Collect | I/T | | R | R | R | R | R/C | | |

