^k Subjects who withdraw from the study anytime during the study will have a follow-up period of 6 months, consisting of an Off-Treatment Safety Follow-up Visit (4 weeks post last dose), telephone call follow-up (3 months post last dose) and ophthalmic assessment (6 months post last dose).

- ^l Subjects will be asked for updates on new and ongoing (after the 28 days follow-up) ocular AEs only.
- ^m Repeat at Off-Treatment Safety Follow-up is only needed if there are outstanding safety concerns from Week 12.
- ^N Score will not be recorded in the database, assessment will be performed for patient safety/monitoring purposes only clinically significant findings will be reported as adverse events.

NOTE: Unscheduled visits may be conducted at any time during the study and may include the same assessments as Week 12.

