2.2.15.2.4 Ocular Treatment Emergent AEs of Special Interest

As defined in protocol Section 9.3.5.5 the following Ocular AEs will be treated as TEAESIs:

- A Class II or Class III grading shift in LOCS III as defined in the Ophthalmology Manual compared to Baseline. A class II or III grading shift will be programmatically derived from the fields captured on the eCRFs in accordance with the Rosiptor Ophthalmology Manual which is the following:
 - Class II: Increase in LOCS III grade of ≥ 0.9 (NO), ≥ 1.0 (C), or ≥ 0.9 (P)
 - Class III: Increase in LOCS III grade of ≥ 1.2 (NO), ≥ 1.5 (C), or ≥ 1.5 (P)
- A reduction of 2 lines or more on the LogMAR chart in BCVA compared to Baseline
- Ocular AEs without clear etiology
- Ocular AEs considered possibly or probably related to study drug

Ocular AEs with clear etiology will be reviewed on a case by case basis to determine if they should be treated as TEAESIs. Ocular TEAESIs will be assessed by an independent, blinded adjudicator.

The number and percentage of subjects who experience a TEAESI will be tabulated by System Organ Class (SOC) and Preferred Term (PT) by treatment group and overall.

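### Ocular AEs starting more than 28 days after last dose are collected to six months but reach the by-arm AE tables only if classed as TEAESIs

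*SAP*

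**What the plan says.** **Reporting rule.** SAP 2.2.15.2 states: "Only those adverse events determined to be treatment emergent (TEAE) will be presented". An event qualifies if it starts after first dosing and, with TEAESIs exempted in brackets, the SAP keeps "only those with an onset date within 28 days after the last date of dosing". Ocular AEs as a class have no exemption.

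**Collection.** Protocol 9.3.5.6 says "Ocular AEs must be followed until the 6-month Ophthalmic Safety Follow-up Visit". That sentence concerns how long events are followed. The collection of new events comes from footnote l of the schedule of events, in both documents: "Subjects will be asked for updates on new and ongoing (after the 28 days follow-up) ocular AEs only". The footnote is attached to the 3-month telephone call and the 6-month ophthalmic visit.

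**Exemption.** Protocol 9.3.5.5 and SAP 2.2.15.2.4 define ocular TEAESIs by four routes: a Class II or III shift in LOCS III; a BCVA loss of two or more LogMAR lines; "Ocular AEs without clear etiology"; and "Ocular AEs considered possibly or probably related to study drug". Ocular AEs with a clear etiology are sorted case by case. TEAESIs then go to an independent, blinded adjudicator.

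**Unblinding.** SAP 2.2.12 places an interim freeze and unblinding after all subjects have completed Week 16. Ophthalmic follow-up results are held for the final lock.

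**The concern.** Protocol 4.2.2.3 makes eye disorders an AE category of interest because of nonclinical findings, and Protocol 4.2.1 reports cataracts in the 26-week rat study. The trial keeps collecting new ocular AEs for five months after other AE collection ends, yet the AE tables use a single 28-day cut-off for every event that is not a TEAESI.

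Whether a late event is counted by arm can then turn on whether its etiology is called clear, how its relationship to drug is rated, and what a case-by-case review decides. A between-arm comparison of late ocular AEs is only as complete as those decisions. If any are made by someone who knows the allocation, entry into the comparison is no longer protected by the blind.

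**Working it through.** **1. Timeline.** Inputs are from Protocol Table 1: end of treatment day 84, off-treatment visit day 112, telephone call day 175, ophthalmic visit day 266.

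- 84 + 28 = 112; 84 + 91 = 175; 84 + 182 = 266. The schedule days agree with 4 weeks, 3 months and 6 months after last dose.

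**2. Untabulated window for non-TEAESI ocular AEs.**

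- Post-dose ocular collection: 266 − 84 = 182 days. Outside the 28-day rule: 266 − 112 = 154 days.
- Share: 154/182 = 84.6%.
- With the ±7-day visit window: 147/175 = 84.0% (day 259) to 161/189 = 85.2% (day 273).

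**3. Which late ocular AEs drop out.** Setting SAP 2.2.15.2 beside 2.2.15.2.4, a late event is excluded only if all of these hold:

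- its etiology is clear;
- it is rated Unlikely related;
- it involves no Class II or III LOCS III shift;
- it involves no BCVA loss of two or more lines;
- the case-by-case review does not upgrade it.

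The two thresholds are numeric, and the SAP derives the LOCS III shift by program. The other three conditions are judgements.

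**4. When the review can happen.** For the last subject to reach Week 16, the 154 days of further ocular follow-up start at the visit that allows the freeze. Apart from the unstated time needed to complete the freeze, his late ocular AEs arise after unblinding. Subjects enrolled earlier are affected less.

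**5. How many events.** The documents give no late ocular AE rate. For illustration only, take the 12-week Eye Disorders incidences in Protocol Table 2 (AQX-1125 16/226, placebo 22/228). Assume a constant rate over a base of 84 or 112 days and 50 subjects per arm:

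- Expected late cases per arm = 50 × [1 − (1 − p)^(154/base)].
- p = 16/226: 6.3 (base 84) or 4.8 (base 112).
- p = 22/228: 8.5 (base 84) or 6.5 (base 112).

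The number left out lies between 0, if all are TEAESIs, and the full 4.8 to 8.5, if none are.

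**6. Does 28 days suit the lens?** Protocol 4.2.1 gives lens half-lives of about 20 days (rat) and 7 to 9 days (dog). Fraction remaining at day 28: 2^(−28/20) = 38% in the rat; 2^(−28/7) = 6% to 2^(−28/9) = 12% in the dog. No human value is given, so this shows only that the cut-off was not evidently chosen with the lens in mind.

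**7. Internal wording.** The sentence restricting presentation to TEAEs is followed, in the same section, by one saying that every reported AE will be tabulated. The SAP synopsis also promises summaries of AEs as well as TEAEs. These cannot all be applied literally.

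**The case against.** The exemption is deliberate and broad: unexplained, possibly or probably related, and threshold-level eye events are counted whenever they start. Lens change is also reported by arm without regard to attribution:

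- SAP 2.2.15.2.5 summarises LOCS III, BCVA, IOP, corneal staining and slit lamp results at six months.
- SAP 2.2.15.2.6 tabulates Class I, II and III events, including Class I shifts below the TEAESI threshold.
- SAP Appendix C models LOCS III to Week 38 with age as a covariate.
- SAP 2.1 lists all data, so with about 50 subjects per arm the remaining events can be read from a listing.

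The 28-day limit also matches the general AE recording period in Protocol 9.3.5.6. Protocol 8.5 keeps investigators and the medical monitor blinded throughout, which protects the investigator's own causality rating.

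Most of this stands. A reader might infer that the plan discards the cataract signal, that an age-attributed cataract goes uncounted, or that 85% of late ocular AEs are dropped. The documents support none of these. A cataract that crosses a LOCS III or BCVA threshold is a TEAESI whatever its attribution, and the 85% is calendar time. Nor do the documents say why the six-month visit exists; the link to the animal findings is a reasonable inference.

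Two things are not answered. A listing and measurement summaries do not give a by-arm count of late ocular AEs. And the documents do not say who carries out the case-by-case review, or that this person is blinded.

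**Conclusion.** The point holds in a limited form. Late ocular AEs that are explained, rated unrelated, below threshold and not upgraded are collected and listed but not counted by arm. The loss is a complete count that is independent of etiology, causality and review decisions, and some of the review can follow unblinding.

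The affected window is 154 of 182 post-dose days (84.0% to 85.2% across the visit window). The number of affected events is unknown: on the constant-rate assumption and 50 per arm it runs from 0 to about 8.5 subjects per arm. This follows from a stated rule, not from missing detail, so it should be corrected, but it does not undermine the ophthalmic safety assessment. Sample size, power and type I error are unaffected.

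**What to change.** - Keep the 28-day window for non-ocular AEs.
- For ocular AEs, either extend the reporting window to the 6-month Ophthalmic Safety Follow-up Visit, or add a by-arm SOC/PT table of all ocular AEs starting more than 28 days after last dose, whatever their TEAESI status.
- State who makes the case-by-case TEAESI decision, and that it is made blinded to treatment, including after the Week 16 freeze.
- Reconcile the TEAE-only sentence in SAP 2.2.15.2 with the later sentence on tabulating every reported AE, and with the synopsis.

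The reporting change takes one SAP sentence and one extra table; the blinding statement and the reconciliation are wording. Ophthalmic results already wait for the final lock, so no analysis is delayed. The downside is that some background, age-related ocular events will enter the counts. They can be read beside the TEAESI table, which stays as planned.
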